13.5 Planned Interim Analysis of the Study

An administrative interim database lock will occur at Week 25 to perform the primary analysis on the first 516 randomized subjects. The purpose of the interim database lock is to provide an analysis of the primary endpoint, safety, PK and immunogenicity up through Week 25 to regulatory agencies before the completion of the study. No trial-related decisions will be made based on the interim analysis. Since no trial-related decisions will be made based on this analysis, the Type I error rate is preserved and no multiplicity adjustment is needed. An interim clinical study report from the interim analysis week 25 (primary endpoint) will be to support regulatory submissions.

The interim analysis will be executed by an unblinded team distinct from the study team. The study team will remain blinded until final database lock. Data to be locked will include efficacy and safety up through Week 25 on the first 516 randomized subjects. The details of the interim analysis, including methodology to maintain the blind of the study team, will be discussed in a separate interim analysis plan.

The final analysis will include the total number of subjects (n=572) and a final clinical study report will be produced accordingly.

14. DIRECT ACCESS TO SOURCE DATA/DOCUMENTS

The investigator/study site will cooperate and provide direct access to study documents and data, including source documentation for monitoring by the study monitor, audits by the sponsor or sponsor's representatives, review by the EC, and inspections by applicable regulatory authorities, as described in the Clinical Study Agreement. If contacted by an applicable regulatory authority, the investigator will notify the sponsor of contact, cooperate with the authority, provide the sponsor with copies of all documents received from the authority, and allow the sponsor to comment on any responses, as described in the Clinical Study Agreement.

15. QUALITY CONTROL AND QUALITY ASSURANCE

15.1 Investigator's Responsibility

The investigator will comply with the protocol (which has been approved/given favorable opinion by the EC), ICH GCP, and applicable regulatory requirements as described in the Clinical Study Agreement. The investigator is ultimately responsible for the conduct of all aspects of the study at the study site and verifies by signature the integrity of all data transmitted to the sponsor. The term “investigator” as used in this protocol as well as in other study documents, refers to the investigator or authorized study personnel that the investigator has designated to perform certain duties. Sub-investigators or other authorized study personnel are eligible to sign for the investigator, except where the investigator's signature is specifically required.

15.1.1 Final Clinical Study Report

The investigator, or coordinating investigator(s) for multicenter studies, will sign the clinical study report. The coordinating investigator will be selected before study start.

15.2 Training

The study monitor will ensure that the investigator and study site personnel understand all requirements of the protocol, the investigational status of the IP, and his/her regulatory responsibilities as an investigator. Training may be provided at an investigator's meeting, at the study site, and/or by instruction manuals. In addition, the study monitor will be available for consultation with the investigator and will serve as the liaison between the study site and the sponsor.

15.3 Monitoring

The study monitor is responsible for ensuring and verifying that each study site conducts the study according to the protocol, standard operating procedures, other written instructions/agreements, ICH GCP, and applicable regulatory guidelines/requirements. The investigator will permit the study monitor to visit the study site at appropriate intervals, as described in the Clinical Study Agreement. Monitoring processes specific to the study will be described in the clinical monitoring plan.

15.4 Auditing

The sponsor and/or sponsor's representatives may conduct audits to evaluate study conduct and compliance with the protocol, standard operating procedures, other written instructions/agreements, ICH GCP, and applicable regulatory guidelines/requirements.

The investigator will permit auditors to visit the study site, as described in the Clinical Study Agreement. Auditing processes specific to the study will be described in the auditing plan.

15.5 Non-Compliance with the Protocol

The investigator may deviate from the protocol only to eliminate an apparent immediate hazard to the subject. In the event(s) of an apparent immediate hazard to the subject, the investigator will notify the sponsor immediately by phone and confirm notification to the sponsor in writing as soon as possible, but within 1 calendar day after the change is implemented. The sponsor (Baxalta) will also ensure the responsible ethics committee is notified of the urgent measures taken in such cases according to local regulations.

If monitoring and/or auditing identify serious and/or persistent non-compliance with the protocol, the sponsor may terminate the investigator's participation. The sponsor will notify the EC and applicable regulatory authorities of any investigator termination.

15.6 Laboratory and Reader Standardization

Not applicable; a central laboratory/reader will be used for all clinical assessments.

16. ETHICS

16.1 Subject Privacy

The investigator will comply with applicable subject privacy regulations/guidance as described in the Clinical Study Agreement.

16.2 Ethics Committee and Regulatory Authorities

Before enrollment of subjects into this study, the protocol, ICF, any promotional material/advertisements, and any other written information to be provided will be reviewed and approved/given favorable opinion by the EC and applicable regulatory authorities. The IB will be provided for review. The EC's composition or a statement that the EC's composition meets applicable regulatory criteria will be documented. The study will commence only upon the sponsor's receipt of approval/favorable opinion from the EC and, if required, upon the sponsor's notification of applicable regulatory authority(ies) approval, as described in the Clinical Study Agreement.

If the protocol or any other information given to the subject is amended, the revised documents will be reviewed and approved/given favorable opinion by the EC and applicable regulatory authorities, where applicable. The protocol amendment will only be implemented upon the sponsor's receipt of approval and, if required, upon the sponsor's notification of applicable regulatory authority(ies) approval.

16.3 Informed Consent

Investigators will choose subjects for enrollment considering the study eligibility criteria. The investigator will exercise no selectivity so that no bias is introduced from this source.

All subjects and/or their legally authorized representative must sign an ICF before entering into the study according to applicable regulatory requirements and ICH GCP. Before use, the ICF will be reviewed by the sponsor and approved by the EC and regulatory authority(ies), where applicable, (see [Section 16.2](#)). The ICF will include a comprehensive explanation of the proposed treatment without any exculpatory statements, in accordance with the elements required by ICH GCP and applicable regulatory requirements. Subjects or their legally authorized representative(s) will be allowed sufficient time to consider participation in the study. By signing the ICF, subjects or their legally authorized representative(s) agree that they will complete all evaluations required by the study, unless they withdraw voluntarily or are terminated from the study for any reason.

The sponsor will provide to the investigator in written form any new information that significantly bears on the subjects' risks associated with IP exposure. The informed consent will be updated, if necessary. This new information and/or revised ICF that has been approved by the applicable EC and regulatory authorities, where applicable, will be provided by the investigator to the subjects who consented to participate in the study.

16.4 Data Monitoring Committee

A Data Monitoring Committee is not used for this study for the following reason:

Subjects are on IP which is the same dose as a product that is already licensed.

The sponsor or designee will be responsible for reviewing accumulating data from the ongoing clinical study on a regular basis.

17. DATA HANDLING AND RECORD KEEPING

17.1 Confidentiality Policy

The investigator will comply with the confidentiality policy as described in the Clinical Study Agreement.

17.2 Study Documentation and Case Report Forms

The investigator will maintain complete and accurate paper format study documentation in a separate file. Study documentation may include information defined as “source data” (see [Section 8.8](#)), records detailing the progress of the study for each subject, signed ICFs, correspondence with the EC and the study monitor/sponsor, enrollment and screening information, eCRFs, SAE reports, laboratory reports (if applicable), and data clarifications requested by the sponsor.

The investigator will comply with the procedures for data recording and reporting. Any corrections to paper study documentation must be done as follows: 1) the first entry will be crossed out entirely, remaining legible; and 2) each correction must be dated and initialed by the person correcting the entry; the use of correction fluid and erasing are prohibited.

The investigator is responsible for the procurement of data and for the quality of data recorded on the eCRFs. The eCRFs will be provided in electronic form.

The handling of data by the sponsor, including data quality assurance, will comply with regulatory guidelines (eg, ICH GCP) and the standard operating procedures of the sponsor.

Data management and control processes specific to the study will be described in the data management plan.

17.3 Document and Data Retention

The investigator will retain study documentation and data (paper and electronic forms) in accordance with applicable regulatory requirements and the document and data retention policy, as described in the Clinical Study Agreement.

18. FINANCING AND INSURANCE

The investigator will comply with investigator financing, investigator/sponsor insurance, and subject compensation policies, if applicable, as described in the Clinical Study Agreement.

[figure not shown]
19. PUBLICATION POLICY

The investigator will comply with the publication policy as described in the Clinical Study Agreement.

20. SUPPLEMENTS

20.1 Study 911401 Schematic

Figure 1
Study Design for Baxalta Clinical Study 911401

*Injections administered subcutaneously at Weeks 0 and 1, and then every 2 weeks in each arm. Last dose at Week 47.

Subjects in Arm B are randomized again 1:1 at Week 16 into Arms B1 and B2.

D = Day; EU RPP = Reference Protein Product; N = number of subjects; PASI = Psoriasis Area and Severity Index.

20.2 Schedule of Study Procedures and Assessments

Table 1
Schedule of Study Procedures and Assessments

Table 1
Schedule of Study Procedures and Assessments

Phase	Screen-ing	Double-Blind Period																			Safety Follow-up ^s
		-4 to 0	0	1	4	8	12	16	17	19	21	25	27	29	33	37	39	41	45	48/ETV	52
Week																					
Study Day		-28 to -1	1	8	29	57	85	113	120	134	148	176	190	204	232	260	274	288	316	337	365
Visit ^r		1	2	3	4	5	6	7	8	9	10	11	12	13	14	15	16	17	18	19	20
Injection training ^m			X																		
Study drug injection onsite ⁿ			X	X						X	X	X	X				X	X			
Post-injection monitoring onsite ^o			X	X						X	X	X	X				X	X			
Injection site evaluation ^p			X	X						X	X	X	X	X	X	X	X	X	X	X	
Study drug dispensing				X	X	X	X	X	X	X	X	X	X	X	X	X	X	X	X		
Study drug return																					X
Study diary dispensing/collection ^q			X										X								X

AE = adverse event; BSA = body surface area; DLQI = Dermatology Life Quality Index; ECG = electrocardiogram; ETV = end of treatment visit; HIV = human immunodeficiency virus; EQ-5D-5L = EuroQoL-5 dimensions- 5 levels; PA: posterior-anterior, PASI = Psoriasis Area and Severity Index; PK = pharmacokinetics; PPD = purified protein derivative; sPGA = static Physician Global Assessment; TB = tuberculosis

^a Inclusion/exclusion criteria to be reviewed before randomization. The screening visit needs to occur with enough time prior to randomization to ensure eligibility requirements for the screening visit are met.

^b Concomitant therapy will include pharmacologic and nonpharmacologic therapies.

^c Subjects in Arm B are randomized again at this visit.

^d Subjects will receive testing if not received within previous 3 months and/or doesn't have documented history of prior positive TB test result or active TB infection. Testing includes QuantiFERON, T-SPOT, or PPD and a radiograph or comparable imaging with negative finding for TB or other similar infections (PA or PA and lateral view).

^e sPGA, PASI and BSA assessments should be conducted at screening and at baseline before randomization and study drug administration to ensure eligibility.

^f All subject-completed assessments (ie, patient-reported outcomes) should be completed before any other assessments are done.

^g Complete physical exam will be conducted at screening, Week 16, and 48. All other physical exams will be brief and should include heart, lungs, abdomen and extremities and skin, and any other assessments required to evaluate AEs.

^h ECG should be recorded before blood sampling.

ⁱ Vital signs should be taken before blood sampling. Height will be measured at Visit 1 only.

Table 1
Schedule of Study Procedures and Assessments

Phase	Screen-ing	Double-Blind Period																		Safety Follow-up ^s	
		-4 to 0	0	1	4	8	12	16	17	19	21	25	27	29	33	37	39	41	45	48/ETV	
Week	-28 to -1	1	8	29	57	85	113	120	134	148	176	190	204	232	260	274	288	316	337	365	
Study Day		1	2	3	4	5	6	7	8	9	10	11	12	13	14	15	16	17	18	19	20
Visit ^r																					

^j PK and immunogenicity blood samples are to be collected in all subjects at these time points. Samples should be obtained prior to administering study drug if an administration occurs at that visit and before any hematology/chemistry samples to be drawn at that visit.

^k Blood samples will be taken before injection of study drug, after ECG and vital signs assessments, and after PK and immunogenicity sampling if applicable.

^l Pregnancy testing is only required for female subjects of childbearing potential. Serum test will be done at screening; all other assessments are done on urine.

^m Self-injection training should be provided with the first injection, with subject or caregiver performing the second injection at the first visit. Additional training can be provided with the Week 1 injection, if needed. At all other visits where the injection occurs in clinic, the subject or caregiver should administer the injection and be observed to ensure correct administration.

ⁿ Study drug will be administered in clinic after all required assessments and blood sample collections have been completed at Weeks 0, 1, 17, 19, 21, 25, 27, 37, and 39. Injections will occur at home in-between clinic visits on Weeks 3, 5, 7, 9, 11, 13, 15, 23, 31, 35, 43 and 47. At Weeks 29, 33, 41, and 45, the study drug injections will be completed at home after the assessments are completed at the clinic.

^o When injection occurs in the clinic, subjects should be observed for a minimum of 2 hours in the clinic after injection at Weeks 0, 1, 17, 25, and 37. Subjects should be observed for 30 minutes after injection at Weeks 19, 21, 27, and 39. At Week 48, only return of study drug will occur.

^p The investigator or a qualified designee will evaluate the current injection sites 30 minutes (\pm 10 minutes) after study drug administration in the clinic at Weeks 0, 1, 17, 19, 21, 25, 27, 37, and 39. They should also evaluate any immediately prior injection site at each subsequent visit as applicable. For injections given at home, injection site reactions will be recorded in the subject diary. There will be no injection at Week 48 (Visit 19), but injection site evaluation for previous injections will occur.

^q The subject should bring the diary at all visits between Weeks 1 and 48. The investigator will review the diary for completeness, request missing information periodically and in a timely manner, photocopy and store the applicable pages in the source documents until the original diary is collected. At Week 25, the subject diary will be collected by the investigator and a new one will be provided until Week 48.

^r Visit windows are \pm 1 day at Visit 3, \pm 3 days for Visits 4-19 and \pm 2 weeks for Visit 20. Reference for visit windows/study day is scheduling based on Visit 2/Baseline Visit.

^s If the subject does not show up to the clinical visit, the site should try to contact the subject by phone for at least 8 weeks after the scheduled follow-up visit and obtain information regarding the occurrence of adverse events, psoriatic and concomitant treatments and pregnancy status. Discontinuing subjects will be invited to perform this visit 5 weeks after last IP dose.

Table 2
Laboratory Parameters

Panel	Parameters	
Hematology	Red blood cell count Hemoglobin Hematocrit Platelet count Mean cell volume White blood cell count (total leucocytes)	Neutrophils (absolute and %) Lymphocytes (absolute and %) Monocytes (absolute and %) Eosinophils (absolute and %) Basophils (absolute and %)
Serum biochemistry	Aspartate transaminase Alanine transaminase Alkaline phosphatase Gamma glutamyl transferase Total bilirubin Lactate dehydrogenase Creatine kinase C-reactive protein Cholesterol Triglycerides Total protein	Sodium Potassium Chloride Bicarbonate Urea Creatinine Albumin Calcium Phosphate Glucose Uric acid
Urinalysis	Leucocytes Protein Bilirubin Urobilinogen Glucose	Ketones Blood pH Nitrite Specific gravity
Urine microscopy	To be done where clinically indicated	
Viral serology	Hepatitis B surface antigen, anti-Hepatitis B surface antigen and anti-Hepatitis B core total (IgG and IgM)	Hepatitis C antibody Human immunodeficiency virus (HIV I and II)
Tuberculosis (TB)	QuantiFERON®-TB Gold test	T-SPOT
Serum/urine pregnancy test	Beta human chorionic gonadotropin	Follicle-stimulating hormone

IgG = immunoglobulin G; IgM = immunoglobulin M.

Table 3
Injection Site Reaction Grading Scheme

Reaction	Intensity Grading				
	Absent (0)	Mild ^a (1)	Moderate ^a (2)	Severe ^a (3)	Potentially Life-threatening (4)
Pain	Absent	Does not interfere with activity	Repeated use of non-narcotic pain reliever >24 hours or interferes with activity	Any use of narcotic pain reliever or prevents daily activity	Hospital visit (A and E) or hospitalization
Tenderness	Absent	Mild discomfort to touch	Discomfort with movement	Significant discomfort at rest	A and E visit or hospitalization
Erythema/ redness	Absent	2.5 to 5.0 cm	5.1 to 10.0 cm	>10.0 cm	Necrosis or exfoliative dermatitis
Induration/ swelling	Absent	2.5 to 5.0 cm and does not interfere with activity	5.1 to 10.0 cm or interferes with activity	>10.0 cm or prevents daily activity	Necrosis
Other ^b	Absent	Present			

A and E = accident and emergency department; AE = adverse event.

^a Measurements refer to the reaction at the greatest single diameter. Measurements of less than 2.5 cm diameter for erythema or induration may be captured as mild per investigator discretion.

^b Any other reactions such as bruising, itching or ulceration will be recorded as absent or present and will be recorded as AEs; AEs will be categorized according to the investigator's judgment, using the guidance presented in [Section 12.1.2](#)

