10.3.2 Treatment Visits

During the double-blind treatment period (Weeks 1 to 48), subjects will return to study site according to the schedule presented in [Table 1](#).

Subjects will self-administer 40 mg of M923 or EU RPP every 2 weeks (Q2W) starting at Week 1 of the study.

Prior to administration of IP, the following assessments will be done at all visits unless otherwise indicated:

- Patient-reported questionnaires: DLQI and EQ-5D-5L (to be completed prior to any other assessments being done [Weeks 16, 25, and 37])
- Review of concomitant medications/non-drug therapies
- AE monitoring
- sPGA, PASI, BSA evaluation

- Brief physical examination (Weeks 4, 8, 17, 19, 25, 27, 37, and 39; complete physical examination at Week 16)
- Vital signs (body temperature, pulse rate, blood pressure, respiratory rate, and measure body weight)
- 12-lead ECG (Weeks 16, 25, and 37)
- PK and immunogenicity (Weeks 8, 16, 17, 21, 25, 29, 37, and 41)
- Clinical laboratory assessments (hematology and serum chemistry; all visits, except Weeks 12, 27, 33, 39, and 45)
- Urinalysis (Weeks 4, 8, 16, 17, 19, 21, 25, and 37)
- Urine pregnancy test (female subjects of childbearing potential only; all visits, except Weeks 1, 19, 27, 39 and 45)
- Study drug dispensing
- Study drug injection in clinic by subject or caregiver (as directed by study site staff)(Weeks 1, 17, 19, 21, 25, 27, 37, and 39)
 - Post-injection monitoring for 2 hours post-injection (clinic only; Weeks 1, 17, 25, and 37)
 - Post-injection observation for 30 minutes post-injection (clinic only; Weeks 19, 21, 27, and 39)
- Study drug injection at home, but after assessments completed at clinic visit (Weeks 29, 33, 41, and 45)
- Study drug injection at home in-between clinic visits (Weeks 3, 5, 7, 9, 11, 13, 15, 23, 31, 35, 43, and 47)
- Injection site evaluation either by clinical staff (at clinic visits) or by the subject or caregiver (administration at home) per [Section 12.10](#)

At Week 16, subjects in Arm B will be randomly assigned again to a new treatment group:

- Arm B1: Continues EU RPP from Weeks 17 through 48 (last dose at Week 47; n = up to 129 subjects)
- Arm B2: Transition to M923 at Week 17; then to EU RPP at Week 25; and to M923 at Week 37 (last dose at Week 47; n = up to 129 subjects)

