13.4.4.3 Pharmacokinetics and Immunogenicity

The methods of analysis for the secondary PK outcome measures (see [Section 8.4.2.3](#)) will be done on the PK population.

The serum levels will be summarized by treatment arm at each scheduled collection. In addition to descriptive statistics described in [Section 13.4](#), the geometric mean, corresponding 95% confidence interval, and the geometric coefficient of variation (CV) will also be presented. To evaluate whether of anti-adalimumab antibody formation will affect exposure, the summaries will be further stratified by ADA formation (subjects who did not form antibodies, subjects who formed ADAs, versus subjects who formed neutralizing ADAs). The within-subject variability (CV) in trough concentrations over time (from Week 17 to Week 41) will be determined for each subject, which will then be compared between treatment arms using an analysis of variance model with treatment as a fixed effect.

The transition from EU RPP to M923 as compared with continuous use of EU RPP with regard to PK will be evaluated using the descriptive statistics at each schedule time point and statistical comparison of within-subject variability.

Pharmacokinetic data from the study may also be used for population PK/pharmacodynamic analyses. If done, a separate analysis plan will be prepared and results will be reported separately from the Clinical Study Report. Population PK/PD analyses are not planned following the administrative interim database lock at Week 25.

The immunogenicity analysis will be done on the safety population.

Immunogenicity data (overall ADA results and titers, and neutralizing ADA results and isotype of ADA where applicable, and time to seroconversion) will be listed. A summary of the number and percent of subjects testing positive for ADA or neutralizing antibodies before the dose of M923 or EU RPP and at scheduled postdose assessments will be presented by treatment arm. The time to seroconversion will be summarized by treatment arm using mean, median, standard deviation and range where appropriate.

The number and percentage of subjects who had at least one ADA-positive result will be provided by treatment arm. Similar analysis may be done for subjects with predose ADA-negative results and with at least one postdose ADA-positive results as appropriate.

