22. SUMMARY OF CHANGES

Protocol 911401 Amendment 3 (Global) 2016 AUG 04

Replaces: Amendment 2: 2015 OCT 08

In this section, changes made in this amendment from the previous version of the protocol, dated 2015 OCT 08, are described and their rationale is given.

1. Throughout the document

Description of Change: Minor grammatical and/or administrative changes have been made.

Purpose for Change: To improve the readability and/or clarity of the protocol.

2. Throughout the document

Description of Change: The following changes were applied to the PK sections of the protocol:

- Section 8.4.2.3: The outcome measure “Exposure to M923 and EU RPP assessed as trough serum levels” was updated to “Exposure to M923 and EU RPP assessed as serum levels”
- Section 11.3: “Blood samples for analysis of serum M923 or EU RPP in terms of trough serum levels will be collected at the times shown in the schedule in Table 1” was changed to “Blood samples for analysis of serum M923 or EU RPP in terms of serum levels will be collected at the times shown in the schedule in Table 1”
- Section 13.4.4.3:
 - “The trough serum levels will be summarized by treatment arm at each scheduled collection” was changed to “The serum levels will be summarized by treatment arm at each scheduled collection”
 - “To evaluate whether of anti-adalimumab antibody formation will affect trough exposure...” was changed to “To evaluate whether of anti-adalimumab antibody formation will affect exposure...”

Purpose for Change: Serum samples through Week 16 are collected at midpoint. For this reason, the term “trough” was removed in the aforementioned sections.

3. Section 1.2 Study Organization

Description of Change: Inclusion of information from the study medical monitors

Purpose for Change: To identify the study medical monitors

4. Section 2 Serious Adverse Event Reporting

Description of Change: Contact for SAE questions changed to “[contact]”

Purpose for Change: This is the specific address for SAE processing, which was considered the ideal destination for SAE reports and queries

5. Section 7.2 Primary objective

Description of Change: Primary objective “to demonstrate equivalent efficacy between M923 (test) and EU RPP (reference) in subjects with moderate to severe chronic plaque-type psoriasis” was changed to “to demonstrate equivalence in measures of efficacy between M923 (test) and EU RPP (reference) in subjects with moderate to severe chronic plaque-type psoriasis”

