5.4 Analysis Periods

Analysis periods will be defined using the two randomization dates. The first analysis period (Week 0 to Week16) is defined from the Week 0 visit to the end of Week 16 visit. The second analysis period (>Week 16) is defined as starting after Week 16 to the end of the study.

For the first analysis period (Week 0 to Week 16), summary tables will be displayed by treatment arm A and B. For the second analysis period (>Week 16), summary tables will be displayed by treatment arm A, B1, and B2.

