9. EVALUATION OF PHARMACOKINETICS

Secondary PK outcome measures will be analyzed using the PK Analysis set.

For the interim analysis, this will include adalimumab concentration and immunogenicity data through Visit 11, Week 25 and will reflect 5 post-dose assessments on Weeks 8, 16, 17, 21 and 25.

Adalimumab serum levels will be summarized by treatment arm at each scheduled collection. In addition to the usual descriptive statistics, the geometric mean, corresponding 95% confidence interval (CI), and geometric coefficient of variation (CV) will also be presented. Concentrations that are below the limit of quantitation (BLQ) will be replaced with the lower limit of quantitation (LLOQ) for the computation of descriptive statistics. Missing concentrations will be treated as missing. Individual and geometric mean (95% CI) adalimumab concentrations will be graphically presented by treatment (A vs B through Week 16 and versus B1 and B2 following re-randomization).

To evaluate whether anti-adalimumab antibody formation will affect exposure, the summaries will be further stratified by ADA formation (subjects who did not form antibodies, subjects who formed ADAs, subjects who did not form neutralizing ADAs, versus subjects who formed neutralizing ADAs), as appropriate.

Figures will be also be generated to display arithmetic mean adalimumab concentrations versus study week grouped by treatment. Scatterplots and boxplots will also present

adalimumab concentrations stratified by ADA status and to explore the relationship between trough concentrations and ADA titres.

The within-subject variability (geometric CV) in trough concentrations (2 weeks postdose samples) over time (Week 17 to Week 41) will be determined for each subject, which will then be listed, summarized, and compared between treatment arms (EU RPP/EU RPP versus EU RPP/M923) using an analysis of variance model with treatment as a fixed effect. For the subgroup in the EU RPP treatment which is randomized to transition to M923 and back, the troughs

- collected in Weeks 21 and 25 fall into the first transition to M923,
- collected in Weeks 29 and 37 fall into the transition back to EU RPP,
- collected in Week 41 falls into the second transition to M923.

The transition from EU RPP to M923 as compared with continuous use of EU RPP with regard to PK will be evaluated using the descriptive statistics at each schedule time point and statistical comparison of within-subject variability.

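### Week 17 results are pre-switch for all of Arm B, but the SAP files them in the post-Week 16 layout (A, B1, B2) and specifies no pooled Arm B summary

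*Protocol*

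**What the plan says.** **Order of events at Week 17.** Footnote n of the schedule (Protocol 20.2, Table 1) reads: "Study drug will be administered in clinic after all required assessments and blood sample collections have been completed at Weeks 0, 1, 17". Footnote j says of PK and immunogenicity samples: "Samples should be obtained prior to administering study drug if an administration occurs at that visit". The home injections are listed in footnote n: "Injections will occur at home in-between clinic visits on Weeks 3, 5, 7, 9, 11, 13, 15, 23, 31, 35, 43 and 47". The last dose before the Week 17 visit is therefore at Week 15. Protocol 8.2 and SAP 2.1 have Arm B2 move to M923 at Week 17. Re-randomisation of Arm B takes place one week earlier, at Week 16.

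**How the results are grouped.** Protocol 13.4.4.3 leaves the grouping open: "The serum levels will be summarized by treatment arm at each scheduled collection". SAP 5.4 settles it: "The second analysis period (>Week 16) is defined as starting after Week 16 to the end of the study". Tables for that period show A, B1 and B2. SAP 9 presents concentrations as "A vs B through Week 16 and versus B1 and B2 following re-randomization". For adverse events, Protocol 13.4.4.2 and SAP 8.1 end Period 1 at Week 16 and run Period 2 from Week 16 to Week 25. SAP 10 uses similar periods for ADA.

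**What SAP 9 says about troughs.** It assigns the Week 21 and Week 25 troughs to B2's first transition to M923. It assigns the Week 17 trough to no transition.

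**The concern.** The analysis boundary follows the re-randomisation date, but treatment does not diverge until the Week 17 dose. Everything measured at the Week 17 visit is thus split by an assignment that has not yet had any effect. Two things follow.

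First, Arm A against all of Arm B, as first randomised, is a valid comparison at Week 17, and for trough concentration it is the only visit that offers it. The plan shows Arm B only in two halves there.

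Second, B2's Week 17 values sit in a layout meant to show what happens after switching. A chance B1/B2 difference at that visit could be read as a switching effect. An ADA result that is positive at Week 17, before any M923, counts in B2's transition period. So do adverse events that start between the Week 16 visit and the Week 17 dose. The transition from EU RPP to M923 is a secondary objective, so the labelling matters.

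**Working it through.** **1. Sampling against dosing.** Doses fall at Week 0 and then at odd weeks from 1 to 47. The on-treatment samples are "PK and immunogenicity (Weeks 8, 16, 17, 21, 25, 29, 37, and 41". Nominal weeks since the last dose, and the last product Arm B2 received:

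| Sample week | Last dose | Weeks since dose | B2's last product |
|---|---|---|---|
| 8 | 7 | 1 | EU RPP |
| 16 | 15 | 1 | EU RPP |
| 17 | 15 | 2 | EU RPP |
| 21 | 19 | 2 | M923 |
| 25 | 23 | 2 | M923 |
| 29 | 27 | 2 | EU RPP |
| 37 | 35 | 2 | EU RPP |
| 41 | 39 | 2 | M923 |

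Weeks 8 and 16 are mid-interval samples. The protocol's reason for removing the word trough agrees: "Serum samples through Week 16 are collected at midpoint". Week 17 is the first 2-week trough, and the only one at which all of Arm B has received nothing but EU RPP. Arms A and B1 are also on the product first assigned at the troughs of Weeks 21, 25, 29, 37 and 41.

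**2. Group sizes.** SAP 2.1 gives 258 in A and 258 in B. A 1:1 split gives 258/2 = 129, which matches the stated maximum of 129 in each of B1 and B2.

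**3. Precision.** With equal SD in the groups, the SE of a difference in means is SD × √(1/n₁ + 1/n₂).

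- A versus pooled B: √(1/258 + 1/258) = 0.0880
- A versus B1, or A versus B2: √(1/258 + 1/129) = 0.1078
- Ratio of SEs: 0.1078/0.0880 = 1.225, so the interval is 22% wider
- Ratio of variances: 1.225² = 1.50

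The 572 subjects actually randomised, taken as 286, 286 and 143, give 0.0836 and 0.1024 and the same ratio.

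**4. Size on the concentration scale.** The documents give no between-subject variability for troughs. Assume a log-scale SD of 0.5, 0.7 or 1.0. The 95% limits on the ratio of geometric means are the estimate multiplied and divided by exp(1.96 × SE):

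| Assumed log SD | A versus one half of B | A versus pooled B |
|---|---|---|
| 0.5 | 1.11 | 1.09 |
| 0.7 | 1.16 | 1.13 |
| 1.0 | 1.24 | 1.19 |

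**5. The boundary at the other switches.** Period 2 includes Week 25 and Period 3 includes Week 37. Injections at those visits also follow the samples, so pre-dose results stay with the product already taken. Only the first switch departs from this, because re-randomisation and the switch dose are a week apart. On the scheduled days, that week (Day 113 to Day 120) is 7 of the 63 days from Week 16 to Week 25 (Day 176), or 11% of Period 2.

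**The case against.** The layout has a stated basis: SAP 5.4 defines its periods by the two randomisation dates. Showing B1 and B2 at Week 17 also gives the pre-switch reference for the B1-versus-B2 comparison, and the within-subject variability analysis in SAP 9 starts at Week 17. Both halves of Arm B are shown, so a reader can combine the summaries, and ADA counts simply add. SAP 5 limits formal testing to the primary outcome and SAP 9 names no A-versus-B1 trough ratio, so the 22% describes an interval that is not specifically planned. PASI, sPGA, ADA and laboratory values are already shown as A versus full B at Week 16, so pooling them a week later adds little. For PK, SAP 9 does not count Week 17 as an M923 trough.

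Most of this stands. It shows that the B1 and B2 columns should be kept and that the loss is small. It does not explain why Arm B as first randomised is not shown at its one common trough, particularly as SAP 5 says treatment differences with 90% and 95% intervals will be displayed for the other outcomes. Nor does it justify counting pre-dose Week 17 ADA results, or adverse events before that dose, as transition-period data in B2.

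A reader might go further and infer that half the EU RPP subjects are lost, that A versus B is biased, or that no other trough is taken on the product first assigned. The documents support none of these. Nobody is excluded, B1 and B2 are random halves of Arm B, and A and B1 have five later troughs on the product first assigned.

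**Conclusion.** The point holds as one of precision and labelling. Week 17 assessments and samples precede the first switch dose, yet the SAP reports them in the second period without pooling Arm B. A versus either half of B has 1.5 times the variance and a 22% wider interval than A versus pooled B, assuming equal SD and a 1:1 split. Under the assumed log SDs, the 95% factor on a trough ratio would fall from 1.11–1.24 to 1.09–1.19. This matters mainly for trough concentration, and the comparison is descriptive.

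For the switch comparison, pre-switch ADA results and events are expected equally often in B1 and B2, so including them dilutes the contrast rather than tilting it. For ADA, the Period 2 count changes only for subjects who are positive at Week 17 and at no later sample in the period.

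The primary PASI75 analysis at Week 16 compares A with the whole of B and is not affected.

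**What to change.** - In SAP 5.4, end the first analysis period, and start the second, at the Week 17 dose, so that Week 17 pre-dose results count as pre-switch.
- Move the Period 1/Period 2 boundary in SAP 8.1 and Protocol 13.4.4.2 to the same point. SAP 10 takes its ADA periods from there, so changing SAP 5.4 alone would leave the documents inconsistent.
- In SAP 9 and 10, add a Week 17 pre-dose summary of Arm A versus pooled Arm B. Keep the B1 and B2 columns at that visit, labelled as a pre-switch reference and balance check.

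No new data are needed. The cost is one extra column at one visit and a period boundary that must be edited consistently in both documents, with a stated rule for subjects who have no Week 17 injection.
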